5.2 EXCLUSION CRITERIA

An individual who meets any of the following criteria will be excluded from participation in this study:

1. Less than 18 years of age
2. Not able to read and write in English or Spanish
3. Resides in a metropolitan area
4. Does not have access to a smartphone and internet
5. Has been diagnosed with diabetes
6. Cannot participate in physical activity as per screener

5.3 LIFESTYLE CONSIDERATIONS

N/A

5.4 SCREEN FAILURES

Screen failures are defined as participants who consent to participate in this study but are not subsequently assigned to the study intervention or entered in the study. Re-screening is permitted if circumstances change.

5.5 STRATEGIES FOR RECRUITMENT AND RETENTION

Participants will be recruited from Community Action Corporation of South Texas (CACOST) health centers through a collaborative effort between CACOST health center employees and the onsite ISA Research Assistant. CACOST is a non-profit organization that aims to improve the health and wellness of the people of South Texas and includes several health services including primary care, women's health, dental, and mental health services. As key healthcare providers in the South Texas region, CACOST is the leading health provider to over 16,000 patients annually. Almost 70% of their patient population is over the age of 18 and 87% of patients identify as Hispanic.

Similar to our successful Phase I recruitment process, recruitment will occur at CACOST clinics and also via CACOST social media platforms. Specifically, Patient Care Coordinators will hand out study flyers prior to patient visits with their primary care physician. The Patient Care Coordinators will instruct interested participants to contact the on-site research assistant for more information about the project and will provide a room number, a telephone number, and hours in which the research assistant is available. Additionally, contact information for the on-site ISA Research Assistant will be listed on study flyers (i.e. online and in person). The same study flyer will also be posted on CACOST social media platforms to further reach the target audience. We successfully used this strategy to recruit rural Hispanic adults from CACOST for focus groups and feasibility testing for the prototype of our proposed diabetes prevention program.

To maximize retention, this study will employ several techniques that have proven successful in previous research projects conducted by ISA with similar populations. First, the on-site ISA Research Assistant will collect as much contact information as the participant feels comfortable providing (e.g., additional phone numbers, email address, preference for calls v. text messages). This will include asking about secondary contacts – these are alternate phone numbers where the participant can be reached, such as the number of a parent, spouse, or friend. To protect participant’s privacy, the on-site Research Assistant will record how the project should be identified when calling each secondary contact (e.g., “the diabetes project” v. “the phone study”). We have successfully retained participants whose personal phones were temporarily unavailable (e.g., the phone was broken or disconnected, the participant got a new number) using this strategy. Second, we will offer reminder texts or calls the day before a scheduled appointment. Third, if a participant misses a scheduled appointment, the on-site Research Assistant will implement the retention protocol with the goal of rescheduling the missed appointment. Specifically, the on-site Research Assistant will contact the participant via their preferred contact method the day of the missed appointment and – if they are not reached – every two business days thereafter for one week. If the participant is not reached within a week, the ISA Research Assistant will begin calling the alternate contacts’ phone numbers. If the participant is not reached after calling each alternate contact once, the Research Assistant will continue contacting the primary number every two days for an additional week. If the participant is not reached after two weeks, the on-site Research Assistant and the Principal Investigator will meet to determine whether additional contacts are warranted or if the participant should be categorized as “lost to follow up.”

In general, we expect the retention rates to be high. CACOST is well regarded in the South Texas region and many participants visit regularly for medical care or other services. We believe the proposed study will have similarly favorable retention rates.

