During Phase I, we developed an early version of a culturally-tailored, theoretically-driven mobile web-based T2D prevention program for rural Hispanic adults. By digitizing our program, we are reducing access barriers and providing diabetes prevention straight to the fingertips of an at-risk population who otherwise would be unexposed to this resource. We aim to increase knowledge about diabetes risk, enhance skills to prevent new cases, and improve self-efficacy to deploy those new skills by interweaving both Hispanic and rural cultural components into our intervention. For example, cultural values like *Familismo*⁸³ will be incorporated by involving *la familia* in healthy cooking nights utilizing traditional Hispanic recipes (e.g. *enchiladas with chicken and low-fat cheese*). PA regimens will be taught in a way that are consistent with rural constraints such as walking at local track fields or being active at home.⁷⁷ Our intervention will capitalize on the strong social support seen among *comadres/compadres*⁸⁴ to encourage healthful behaviors and change social norms on rural exercise.⁷⁸⁻⁷⁹ Further, interactive tools that promote self-regulation (e.g. goal setting tool) will provide motivation to end-users and increase self-efficacy to adopt and maintain healthy eating and PA. In developing an mHealth diabetes prevention program, we are providing a scalable resource that can make a significant impact on Hispanic health, thus, presenting vast commercialization potential across rural America.

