5 STUDY POPULATION

5.1 INCLUSION CRITERIA

In order to be eligible to participate in this study, an individual must meet all of the following criteria:

1. Provision of signed and dated informed consent form
2. 18 years of age and older

3. Able to read and write in English or Spanish
4. Hispanic
5. Resides in rural area
6. Has access to a smartphone and internet access
7. Does not have diabetes
8. Has prediabetes as per screener
9. Not currently pregnant
10. Can participate in physical activity as per screener

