7.2 PARTICIPANT DISCONTINUATION/WITHDRAWAL FROM THE STUDY

Participants are free to withdraw from participation in the study at any time upon request.

An investigator may discontinue a participant from the study for the following reasons:

- Lost-to-follow up; unable to contact subject
- Participant withdraws consent for further participation and/or data use.
- Safety concerns: any SAE or AE judged related to participation that warrants removal, per the Data and Safety Monitoring Plan and IRB reporting rules.
- Ineligibility discovered post-enrollment, duplicate enrollment, or other protocol violations that compromise data integrity.
- Investigator decision that continued participation poses undue burden or risk (e.g., credible threats of harm), consistent with IRB policies.

The reason for participant discontinuation or withdrawal from the study will be recorded on a dedicated Case Report Form (CRF). Participants who withdraw or are discontinued after randomization will not be replaced; enrollment continues until the target sample size is reached.

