9.2 SAMPLE SIZE DETERMINATION

We examined power using treatment effects from two sources: 1) a meta-analysis examining the overall effectiveness of mobile device interventions on weight loss¹⁵⁴ and 2) a digital diabetes prevention program for low-income patients.⁸⁵ First, a meta-analysis examining the effects of mobile device interventions on weight loss found an average effect size of Cohen's d : 0.43 (95% CI:0.252-0.609; $p < 0.01$) across 11 mobile-based intervention studies.¹⁵⁴ This indicates an overall medium effect size. Second, Kim et al.⁸² developed and tested a mobile-based diabetes prevention program for a multi-racial/ethnic population. This study yielded a mean weight loss of 4.4% (SD 7.7%) at 12 months. This finding is associated with a Cohen's d =0.57, which is considered a medium effect size. To ensure our study is fully powered, we conducted our power analysis using the smaller effect size (Cohen's d =0.43) from Lyzwinski et al.¹⁵⁴, who examined the effects of mobile-based interventions on our primary outcome, participant weight loss.

We estimated power for the paired t-test for %weight loss (primary outcome). The G*Power 3.1 program¹⁵⁷ was used to determine that a Cohen's d of 0.43 and an α error probability of 0.05 requires a final sample size of 136 to be sufficiently powered ($1 - \beta$ error probability) at 0.80. Presuming a 20% attrition rate, randomizing a final sample size of 164 participants should be sufficient to detect significant differences in % weight loss across the two survey time points (i.e., at baseline and 3 months after the end of the intervention).

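### Former testers of the STEPS prototype can be randomised to either arm, because no eligibility criterion, screening question or baseline item covers earlier exposure.

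*Combined protocol and SAP*

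**What the plan says.** Section 2.2 (Background) describes the Phase I product as a forerunner of the present programme: "During Phase I, we developed an early version of a culturally-tailored, theoretically-driven mobile web-based T2D prevention program for rural Hispanic adults".

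Section 5.5 ties the two phases to one recruitment route: "Similar to our successful Phase I recruitment process, recruitment will occur at CACOST clinics and also via CACOST social media platforms". It then reports that this strategy served to "recruit rural Hispanic adults from CACOST for focus groups and feasibility testing for the prototype of our proposed diabetes prevention program". Provider, channels and target group are therefore shared.

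Section 5.1 lists ten inclusion criteria and Section 5.2 six exclusion criteria. The exclusions cover age, literacy, metropolitan residence, lack of a smartphone and internet, diagnosed diabetes, and inability to take part in physical activity. Neither list mentions Phase I or earlier use of STEPS. The screening steps and baseline measures in Section 8.1 do not ask about it. Section 6.3 does not stratify on it, and Sections 9.3 to 9.4.5 do not name it.

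The nearest rule is a discontinuation reason in Section 7.2: "Ineligibility discovered post-enrollment, duplicate enrollment, or other protocol violations that compromise data integrity". It does not extend to taking part in the earlier phase.

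**The concern.** People who tested the prototype have already answered this recruitment strategy once, and Section 5.5 notes that many participants visit the provider regularly. Some may well answer the new flyer. As written, the plan would enrol them without anyone knowing.

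A former tester in usual care is not a clean control if what was learned in Phase I still influences knowledge or behaviour. A former tester in the STEPS arm may have less left to gain after baseline. Either mechanism would shrink the difference between arms.

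Diabetes knowledge is the endpoint most open to this, because learning carries over and can already be present in the baseline score. For percent weight loss the mechanism needs more. Weight lost before the trial's own baseline does not count, so earlier exposure matters only if it reduces the further response to STEPS or is still changing behaviour among controls during follow-up.

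**Working it through.** **Inputs from the documents**
- Planning effect and error rate (Section 9.2): "Cohen's d of 0.43 and an α error probability of 0.05".
- 136 evaluable at power 0.80, 20% attrition, 164 randomised (Section 9.2).
- Two-tailed test at 5% (Section 9.4.2); 1:1 allocation (Section 6.3).

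**Not in the documents:** the number of Phase I participants, how many used the prototype and how many only joined a focus group, and the time since Phase I. The overlap and the carry-over below are therefore assumptions, shown as a range.

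**Step 1. The plan's own figure.** A two-sample t-test with d = 0.43 and power 0.80 needs 68 per arm, or 136 in total, at one-sided 5%. At two-sided 5% it needs 86 per arm, or 172. So 136 reproduces only as a one-sided figure. The 164 is 136 × 1.2 (163.2, rounded up). After 20% attrition that leaves 164 × 0.8 = 131.2, or 65.6 per arm.

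**Step 2. Reference power without overlap.** At 65.6 per arm, d = 0.43 and two-sided 5%, power is 68.6%. The distance from 80% comes from the one-sided calculation and the attrition step and has nothing to do with Phase I. Only the change from 68.6% belongs to this point.

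**Step 3. Dilution.** Let f be the share of the sample with earlier exposure and r the share of the effect they still show. Then

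d_eff = 0.43 × [1 − f(1 − r)]

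| f | about how many of 164 | r = 0: d_eff, power (loss in points) | r = 0.5: d_eff, power (loss in points) |
|---|---|---|---|
| 0 | 0 | 0.430, 68.6% | 0.430, 68.6% |
| 1% | 2 | 0.426, 67.7% (0.9) | 0.428, 68.2% (0.4) |
| 2% | 3 | 0.421, 66.8% (1.8) | 0.426, 67.7% (0.9) |
| 5% | 8 | 0.409, 64.1% (4.5) | 0.419, 66.4% (2.2) |

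With 68 per arm in place of 65.6, the two-sided losses are the same to within 0.1 point.

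**Step 4. How large could f be?** Section 5.5 gives over 16,000 patients a year, almost 70% adult and 87% Hispanic: 16,000 × 0.70 × 0.87 ≈ 9,700. Suppose Phase I participants enrolled at the same rate as everyone else. Then 20, 50 or 100 of them (illustrative counts) would supply 164/9,744 × 20, 50 or 100, or about 0.3, 0.8 or 1.7 of the 164. The pool is not cut down for prediabetes, rural residence or smartphone access, and former testers may respond more readily than others, so the true share could be higher. A share of 5% would need about 8 of them in the trial.

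**The case against.** The case against is strong on size. Phase I exposed people to an early version, and some may only have sat in a focus group. No document says that anyone received the 12-module programme with tracker and text messages. The direction for weight is not settled either: a former tester in usual care who is regaining weight would widen the contrast, and one in the STEPS arm might engage better through familiarity. Under equal response the overlap is one or two people. All of this stands, and it limits the point to a small one.

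A reader might infer more than the documents support:
- That people who have already had STEPS will enter the trial and certainly pull the primary result toward no effect. The documents show that they can enter. They do not show how many will, or that weight loss from the trial's baseline would be attenuated.
- That one arm gains. Prior exposure precedes randomisation and is balanced in expectation.
- That overlap of 10% or 15% is a realistic planning case. At 15% about 25 of 164 would be former testers, and nothing in the documents supports that.
- That power in the sixties is the result of this gap. Almost all of the distance from 80% is the separate sample-size matter in Step 1.
- That the problem could never be detected. It can be, if prior exposure is recorded.

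The protocol mixes past and future tense, so enrolment may already have begun or ended. In that case a new exclusion helps only partly or not at all, and the recording step has to carry the fix.

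**Conclusion.** The gap is real: the recruitment route is shared, the product tested there was a prototype of the same programme, and no part of the plan excludes, records or handles earlier exposure. It is a cheap improvement to enrolment and does not show that the primary comparison is invalid.

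The plausible cost is roughly 1 to 4.5 points of two-sided power at 1% to 5% overlap if former testers show no contrast, and about half that if they keep half the effect. This rests on the assumed overlap, on the assumed carry-over, and on d = 0.43 applying to everyone else. For percent weight loss, even the presence of attenuation is an assumption. For diabetes knowledge it is more plausible, but the documents give no planning effect for that endpoint, so no figure can be put on it.

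**What to change.** **If enrolment is open.** Add an exclusion to Section 5.2 for anyone who took part in Phase I feasibility testing of STEPS or has used any earlier version of it, and put one matching question in the pre-screener. Record Phase I focus-group participation as a baseline item; it need not exclude.

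**For anyone already randomised.** Record prior exposure in the same way in both arms, from Phase I records where they exist, since recall after an unblinded allocation could differ by arm. Do this before the linking file is wiped at the end of follow-up (Sections 2.3.3 and 10.1.3), because matching may be impossible afterwards. Report the count by arm. Keep the intention-to-treat analysis of Section 9.3 as primary, and pre-specify a sensitivity analysis of percent weight loss and diabetes knowledge without the exposed participants. Exposure precedes randomisation, so leaving them out by that criterion keeps the comparison randomised.

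**Cost.** One criterion, one screening question, one baseline item and one sensitivity analysis. A few otherwise eligible people are lost from a provider that sees over 16,000 patients a year.

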6 STUDY INTERVENTION(S) OR EXPERIMENTAL MANIPULATION(S)

No text is to be entered in this section; rather it should be included under the relevant subheadings below.

6.1 STUDY INTERVENTION(S) OR EXPERIMENTAL MANIPULATION(S) ADMINISTRATION

No text is to be entered in this section; rather it should be included under the relevant subheadings below.

6.1.1 STUDY INTERVENTION OR EXPERIMENTAL MANIPULATION DESCRIPTION

STEPS is an effective, affordable, and scalable intervention to reduce Type II Diabetes risk in Hispanic adults. Principles from the Social Cognitive Theory (SCT),^{53,84,117} Theories of Social Networks and Social Support¹¹⁷ will guide development of **STEPS**. For example, self-regulation is a core concept of SCT¹¹⁷ and a key component of T2D prevention.⁹⁸ As such, **STEPS** will include interactive tools to help end-users set PA and eating goals, monitor progress towards meeting those goals, and reinforce success through feedback. Additionally, outcome expectations related to T2D diagnosis and outcomes will be examined through a cultural lens. There will be substantial observational learning opportunities through videos and interactive activities that will also reinforce self-efficacy in healthy eating and PA. Additionally, the Theories of Social Networks and Social Support¹¹⁷ will provide a framework to mobilize social resources at both the individual and community levels. Our tool, Connect with Comadres/Compadres, will encourage social network appraisal and help users solicit instrumental support to meet their health goals. Lastly, the FiLLM⁵⁰ model will guide cultural tailoring of **STEPS** to meet the needs of rural Hispanics.

The **STEPS** 12-week curriculum closely follows the sequence and topics of the original DPP intervention.⁴⁹ Van Name et al¹¹⁸ conducted an RCT on a shortened (14-wk) version of the DPP. At 12-month follow up, participants who received this modified DPP yielded a 6% weight loss as compared to controls. Building off this success, we intend to incorporate all core behavioral learning components of successful intensive lifestyle intervention for T2D.⁹⁸ The first seven modules will focus on building foundational knowledge, setting and then working towards diabetes preventive goals, and enhancing self-monitoring skills. The latter five modules will focus on maintenance of behavior change. All module content will address the psychological, social, and motivational benefits and barriers to regular PA and healthy eating specifically among rural Hispanics.

Self-monitoring and social support are integral components of self-regulation, and are critical to effective diabetes prevention.⁹⁸ The *Goal Setting* tool will utilize a simple interface with drop down options and buttons to easily help users define specific and attainable PA and healthy eating goals.⁹⁸ Specifically, end-users will be able to 1) name their goal, 2) type in the behavior (e.g., walk two laps at the track), and 3) select the frequency (e.g., 3 times per week) and duration (e.g., 4 weeks) of the desired behavior. The *Goal Setting* tool will then finalize their goal (e.g., “I will walk two laps at the track 3 times a week for 4 weeks.”) This tool will allow users to easily monitoring their goals (e.g. indicate goal progression and completion). Once a goal is achieved, users will receive a virtual trophy icon by their goal to indicate success. The **STEPS Tracker** is a highly interactive tool that is synced with a Fitbit wearable and allows for self-monitoring of PA, diet, and weight. Within the tool, users can set their daily steps goal, will see visuals on their progress (via the Fitbit web API), and will receive notifications for achievements. Additionally, users can manually enter their weight and daily dietary consumption by selecting foods from a library of common and cultural foods. Users will receive summary statistics and figures displaying calories and fat per food item and each day’s consumption, aligned with the original

DPP curriculum.⁴⁹ The **STEPS Tracker** will provide visual feedback with charts and easy to understand diagrams (e.g. total steps walked per day and per week). The *Connect with Comadres /Compadres* tool will allow users to create friend groups within the **STEPS** program and then exchange support, motivation, and successes by using pre-designed messages (e.g. “You’ve got this”, “Great job”). In addition, users will be able to post their daily steps from the **STEPS tracker** tool within their friend groups to show successes and encourage others in their PA endeavors. The *Health Text Messages* tool will deliver 46 text messages across the intervention. A meta-analysis examining the effects of text-messaging for health promotion found that message frequency moderated the effect of health interventions.¹²⁰ Specifically, interventions that decreased the frequency of text messages had larger effects than those that relied on low-fixed or high-fixed messaging frequency. Thus, **STEPS** users will receive 5 messages per week during week 1, 4 messages per week during weeks 3-8, and 3 messages per week during weeks 9-12. Topics will cover healthy eating, PA, stress, motivation, and reminders to use the program. Examples of text messages include: “*Make tonight a healthy eating night con la familia! Check out the healthy arroz con pollo recipe in **STEPS**: <weblink>*”; “*Stand up and walk in place for 5 minutes!*”; and “*Take a minute to do belly breathing. Try this exercise in **STEPS** <weblink>*”.

The control group will receive usual care.

6.1.2 ADMINISTRATION AND/OR DOSING

Participants in the intervention arm receive a fully automated, mobile web app that videos, text, animations, and interactive activities. It is entirely accessible on a mobile device. The curriculum phase consists of twelve modules that are adapted from the DPP and also align with Effective components of Lifestyle Interventions to Reduce Diabetes Risk. These effective components include: Commit to Program; Set Goals, Self-monitor (diet, weight, PA); Reduce overall calorie intake; Build healthier eating patterns; Increase PA, reduce sedentary time; Self-regulate energy balance; Manage environmental cues (stimulus control); Problem Solving; Manage self-defeating thoughts, lapses; Manage social cues, build social support; and Manage motivation, stress, health overall.

Curriculum frequency/intensity. The curriculum comprises 12 modules; for dose accounting, we treat each module as a “session,” yielding ~12 sessions for a full curriculum dose (with additional tools available or usage).

There are **no live interventionists** and **no participant-to-participant interaction** after randomization. All contact is and web-based and a pre-recorded Community Health Worker hosts the videos. There is no face-to-face or group sessions conducted.

Control arm receives usual care.

